w The Bayley-III will be administered to patients from 1 month of age until the maximum score on each of the 3 administered scales has been obtained. Once the maximum score for a scale has been achieved, only the remaining scales will be administered. Bayley-III is to be discontinued when the patient reaches 42 months of age. Leiter-3 Scale assessment is to be performed at the last assessment of the Bayley-III Scales prior to the patient reaching 42 months of age. In case the developmental level of an individual patient is below the level required for the Leiter-3 Scale assessment, the patients should be assessed by the Bayley-III regardless of the patient's age.

x Hearing testing includes audiogram and brainstem auditory evoked potentials.

y Separate informed consent will be sought to permit for the acquisition and use of photographs of the patient's eyes in order to allow for independent review of eyelid position measurements by central reader.

z PedsQL Generic Core Scales will be used in pediatric patients 2 years and older, using age appropriate reports

aa Pain will be assessed by PedsQL Pediatric Pain Questionnaire for patients >5 years of age. Observer reported Pain VAS will be recorded in patients of all ages.

bb Pulmonary function tests are not required for patients unable to reliably undergo testing or for patients who are invasively ventilated; reading will be done by central reader.

cc 6MWT in patients who are able to ambulate at least 40 meters (approximately 130 feet) without stopping and without an assistive device.

1.2.2 Extension period (Week 27 to Week 35) including details for Stage 2 - Cohort 3 for patients switching to alglucosidase alfa

Period	Extension Period					
Day(D) or Week (W)	W27	W28	W29	W31	W33	W35
Visit	V16	V17 ^a	V18	V19	V20	V21
Visit at clinical site ^b	X	X	X	X	X	X
Concomitant medications/therapies	X	X	X	X	X	X
IRT contact (Dispensing)	X		X	X	X	X
Study treatment administration						
alglucosidase alfa	X		X	X	X	X
Safety						
Urine pregnancy test ^c			X		X	
Physical examination ^d			X ^a		X ^a	
Body weight	X ^a		X		X	
Vital signs ^e	X		X	X	X	X
ECG ^f			X ^a			
Biochemistry ^g		X	X		X	
Anti-alglucosidase alfa antibodies (with testing for neutralizing antibodies in anti-alglucosidase alfa antibody positive patients) ^h		X	X ^a		X ^a	
Adverse event collection	X	X	X	X	X	X
Pharmacokineticsⁱ						
alglucosidase alfa plasma samples	X ^a					
Efficacy						
Ventilator use diary ^j	X		X	X	X	X

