10.1.2.6 Every 3 months

The following assessments will be performed at quarterly visits (W13 and W25):

- Physical examination;
- Body weight;
- Height/body length/head circumference;
- Lab:
 - Urine β -HCG pregnancy test (females of childbearing potential only);
 - Safety:
 - Hematology, biochemistry, and urinalysis;
 - ADAs (with neutralizing antibodies in ADA-positive patients) for anti-avalglucosidase alfa and anti-alglucosidase alfa antibodies for patients receiving avalglucosidase alfa, and anti-alglucosidase alfa antibodies only for patients in Stage 2-Cohort 3, who are randomized to receive alglucosidase alfa treatment at current stable dose (W13 only);
 - ADAs (with neutralizing antibodies in ADA positive patients) for anti-avalglucosidase alfa and anti-alglucosidase alfa antibodies (W25 only);
 - Biomarkers:
 - [REDACTED]
 - [REDACTED]
 - [REDACTED]
 - Urine Hex4 sample collection;

- Avalglucosidase alfa plasma PK sample collection (before and following infusion) in patients receiving avalglucosidase alfa;
 - For Cohort 1 and 2 patients and for Cohort 3 patients who are randomized in the avalglucosidase alfa group, this visit requires a stay at the site prior to and for at least 8 hours following the end of IMP infusion (Week 25 only).
 - For Cohort 2 patients and for Cohort 3 patients who are randomized in the avalglucosidase alfa group, another sample will be taken 12 to 16 hours after the end of IMP infusion (Week 25 only). If the Cohort 3 dose of avalglucosidase alfa is 20 mg/kg qow, this additional sample will not be taken.
- Blood samples will be obtained as blood volume permits and will not exceed the blood volume collection limit of < 7 mL/kg over an 8-week period. Sampling is prioritized for safety labs (hematology, biochemistry, ADA) and PK and [REDACTED]
[REDACTED]
[REDACTED]
[REDACTED]
- ECG;
- Vital signs (before, during, and following infusion: see [Section 1.2](#));
- Muscle biopsy (optional) at Week 25 only;
- Ventilator use diary;
- PFT (in patients who can reliably undergo testing and/or who are not invasively ventilated);
- 6MWT (in patients who are able to ambulate at least 40 meters [approximately 130 feet] without stopping and without an assistive device);
- GMFM-88/GMFCS-E&R
- Motor Skills Checklist;
- QMFT;
- Pompe-PEDI, Functional Skills Scale: Mobility Domain;
- Bayley-III/Leiter-3 scales;
- Echocardiography;
- Hearing testing;
- Eyelid position measurements;

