2.1.9 Tertiary endpoints

Tertiary endpoints include:

Six-minute walk test

The 6MWT will be performed to assess functional capacity for patients who are ambulatory, defined as the ability to ambulate 40 m (approximately 130 feet) without stopping and without an assistive mobility device. The primary outcome measure of the 6MWT is the distance walked in 6 minutes recorded in meters. Test equipment and administration techniques will be standardized among the investigational sites. The percent (%) predicted value will be calculated based on the normal reference equations from Table 2 (3) (4), which cover the age range in this study. A similar approach was used by Montes et al (5). For analysis purposes, the age at each assessment will be calculated based on (assessment date - birth date + 1)/365.25. Height (which is to be assessed annually for patients with age ≥ 18 years and every 3 months for patients with age < 18 years) will be based on the most recent valid value at or prior to the assessment date.

Table 2 - Equations for calculating reference value for percent predicted total distance walked in 6MWT

Reference	Age at baseline	Gender	Equation
(3)	≥ 18 years	Male and Female	$868.8 - 2.99 * \text{age} - 74.7 * \text{sex}$
(4)	< 18 years	Male	$196.72 + 39.81 * \text{age} - 1.36 * \text{age}^2 + 132.28 * \text{height}$
	< 18 years	Female	$188.61 + 51.50 * \text{age} - 1.86 * \text{age}^2 + 86.10 * \text{height}$

Age in years; sex = 0 if male and sex = 1 if female; height in meters.

Additional information, including the amount of time walked (to quantify endurance, as all patients may not complete the full 6-minute walk), as well as the use and change from baseline in

assistive mobility devices (including straight cane, wide-based cane, one crutch, two crutches, standard walker, rolling walker, orthotics and other) will also be reported.

Pulmonary function testing

The PFT will include the assessment of FVC, forced expiratory volume in the first second of the FVC maneuver (FEV1), maximal inspiratory pressure (MIP), maximal expiratory pressure (MEP), and peak expiratory flow in the upright and supine positions. Pulmonary function tests are not required for young patients unable to reliably undergo testing or for patients who are invasively ventilated, but missing assessments must be documented for analysis and potential impact on the study results.

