2.4.8 Analyses of efficacy endpoints

To evaluate the effect of switching to avalglucosidase alfa after having received alglucosidase alfa at current stable dose, comparative assessment on a composite score and several other efficacy endpoints will be conducted using the mITT population.

All efficacy endpoints defined in [Section 2.1.6](#) will be summarized descriptive by dose cohort and treatment group. For 6MWT results, descriptive summary will only be provided for those complete the 6 minutes walk test.

The mean composite scores between avalglucosidase alfa and alglucosidase alfa patients will be compared. The difference in average composite scores between avalglucosidase alfa and alglucosidase alfa patients will be used as the test statistic, and calculate a p-value. The null and alternative hypotheses for the primary efficacy endpoint are described as H_0 and H_a below:

H_0 : Mean Composite Score for avalglucosidase alfa = Mean Composite Score for alglucosidase alfa; versus

H_a : Mean Composite Score for avalglucosidase alfa \neq Mean Composite Score for alglucosidase alfa

The difference in average composite scores between avalglucosidase alfa and alglucosidase alfa patients will be used as the test statistic.

The control arm (alglucosidase alfa treatment) in Cohort 3 will serve as a reference. If deemed appropriate, these analysis might be repeated using Cohort 2 and/or Cohort 1 patients combined with Cohort 3 avalglucosidase alfa treated patients.

Statistical inference will be performed based on the re-randomization approach. Specifically, all possible randomization sequences that are consistent with the selected randomization design (i.e., stratified randomization stratifying on gender) will be generated, the test statistics will be calculated for all randomization sequences, and the statistical significance level will be calculated as the proportion of more or equally extreme scenarios than the observed one, among all possible scenarios. Due to the small sample size and open-label nature, p-values will serve as references only and any interpretations should be made with caution.

Similar re-randomization test might be performed for other efficacy endpoints.

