2.5.2 Missing data handling in data presentation

In general, missing baselines will not be imputed. The following approaches are default methods for missing data handling in summary tables.

- Categorical data at baseline will be summarized for each treatment group using n and %. Denominator will be the analysis population specified for the summary, unless otherwise specified. Missing data may be presented as a separate category.

- Continuous data: The analyses and summaries for variables with continuous scales will be based on observed data only.

Handling of computation of treatment duration if investigational medicinal product end of treatment date is missing

For the calculation of the treatment duration, the date of the last dose of IMP is equal to the date of last administration reported on drug exposure e-CRF page. If this date is missing, then the duration is missing.

The last dose intake should be clearly identified in the e-CRF and should not be approximated by the last returned package date.

Handling of missing/partial dates for adverse events or concomitant medications

Missing or partial AE onset dates and times will be imputed so that if the partial AE onset date/time information does not indicate that the AE started prior to treatment or after the treatment-emergent adverse event period, the AE will be classified as treatment-emergent. No imputation of AE end dates/times will be performed. These data imputations are for categorization purpose only and will not be used in listings. No imputation is planned for date/time of AE resolution.

No imputation for medication start/end dates or times will be performed. If a medication date or time is missing or partially missing and it cannot be determined whether it was taken prior or concomitantly, it will be considered a prior, concomitant, and post-treatment medication.

Handling of missing or partial birth date for calculation of age

Complete missing of birth date is not expected for the study. However, there could be rare situations in which the birth day or month is not provided for the patient due to confidentiality. In this case, the missing day will be imputed as 15th of the month, and missing month will be imputed as June as default. The adjustment may be needed in the case of conflicting with study dates. These adjustments should be very rare and will be documented in the data specification document.

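### By-visit 6MWT and lung function summaries can look better than the cohort's true course if a child tested at baseline later becomes untestable through disease

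*SAP*

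**What the plan says.** **Who is tested.** The flow chart footnote in Protocol 1.2.1 specifies "6MWT in patients who are able to ambulate at least 40 meters (approximately 130 feet) without stopping and without an assistive device". The same condition is restated for the later visits in Protocol 10.1.2.6, 10.1.3.7 and 10.1.4.5, so it applies afresh each time. SAP 2.1.9 agrees: "The 6MWT will be performed to assess functional capacity for patients who are ambulatory". For lung function, SAP 2.1.9 says "Pulmonary function tests are not required for young patients unable to reliably undergo testing or for patients who are invasively ventilated", as does Protocol 9.3.3.1.

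**How the values are summarised.** SAP 2.4.10 summarises tertiary endpoints by visit, as observed values and changes from baseline, by cohort and arm. SAP 2.5.2 sets the default for continuous data: "The analyses and summaries for variables with continuous scales will be based on observed data only".

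**What is said about missing values.** For PFT, SAP 2.1.9 adds that "missing assessments must be documented for analysis and potential impact on the study results". SAP 2.4.8, 2.4.10 and 2.5.2 contain no analysis that uses this documentation. The documents state no matching requirement for a 6MWT that is not done. The Week 25 carry-forward and the zero for a missing baseline in SAP 2.5.2 apply to the composite score only.

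**The concern.** A value that is absent because the child got worse is not missing at random. If a child who walked at baseline stops meeting the 40 m criterion, or a child with baseline spirometry goes onto invasive ventilation, the by-visit mean is then taken over the children who did better. The table shows a smaller n but not the reason for it. If such losses differ between arms or cohorts, the distortion differs too.

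Functional endurance and respiratory function are among the other objectives (Protocol 5.3, SAP 1.2.3). Week 25 changes in 6MWT distance, FVC, MIP and MEP also feed the antibody scatter plots (SAP 2.4.5) and may feed the correlations between endpoints (SAP 2.4.10.1), so the same selection carries into those displays.

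This is separate from the SAP 2.4.8 rule "For 6MWT results, descriptive summary will only be provided for those complete the 6 minutes walk test". That rule removes children who start the walk and stop early. The present point concerns children who are not tested at all, and changing that rule would not bring them back.

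**Working it through.** The plan gives no sample size calculation, effect size or rate of decline for 6MWT or PFT, so there is no figure of its own to reproduce. What follows illustrates how sensitive the tables are.

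**Input from the documents.** Cohort 3 randomises at least 10 children 1:1, so about 5 per arm (SAP 1.1). Cohorts 1 and 2 have at least 5 each. The number able to walk 40 m or do spirometry is not stated and may be smaller.

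**Assumed inputs.** n children tested at baseline, L of them later untestable, baseline distance B, change c in the other children, and a fall F in FVC % predicted for a newly ventilated child.

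**6MWT, others unchanged (c = 0), B = 300 m, L = 1.** The observed-only mean change is 0 m. With the lost walker scored 0 m it is -L x B / n:
- n = 5: -300/5 = -60 m
- n = 6: -300/6 = -50 m
- n = 10: -300/10 = -30 m

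**6MWT, others gain 10 m (c = 10), L = 1.** The observed-only mean change is +10 m. With the lost walker scored 0 m it is ((n - L) x c - L x B) / n:

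| B | n = 5 | n = 10 |
|---|---|---|
| 150 m | (40 - 150)/5 = -22 m | (90 - 150)/10 = -6 m |
| 300 m | (40 - 300)/5 = -52 m | (90 - 300)/10 = -21 m |
| 450 m | (40 - 450)/5 = -82 m | (90 - 450)/10 = -36 m |

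The gap is L x (c + B) / n, which is 32 to 92 m for n = 5. The sign reverses in every cell.

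**FVC % predicted, others unchanged, n = 5, L = 1.** The observed-only mean change is 0. Counting the child gives -F/5, which is -3, -6 or -12 points for F = 15, 30 or 60.

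**How likely is at least one such child?** For an assumed risk p per child, the chance among 5 is 1 - (1 - p)^5: 23%, 41% or 67% for p = 5%, 10% or 20%.

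**What a worst-rank median does.** With one of five lost, the observed-only median is the midpoint of the second and third of four values. Ranking the lost child worst moves it to the second-lowest of those four. If the other four all change by the same amount, the median does not move. With three of five lost, the median child is untestable. It needs no invented distance, but it is less sensitive to a single loss than a mean, so it should stand beside a count and not replace one.

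**The case against.** A reader might infer that lung function and walking distance are never measured once a child is ventilated or needs help to walk, that the sickest children therefore vanish from the results, and that the means will look better. The documents do not support that reading.

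- **Testing is not barred.** PFT is described as not required under invasive ventilation, which leaves it possible. For the walk, Protocol 9.3.3.2 allows a cane or walker during the assessment and records changes in device use, and SAP 2.1.9 reports them. A child who comes to need a device may still contribute a distance.
- **The shift is conditional.** It needs a child with a baseline value who then deteriorates past one of the two lines. No rate is given. The effect on a difference between arms depends on which arm loses more.
- **The decline is recorded elsewhere.** GMFM-88 and GMFCS-E&R are secondary endpoints with no 40 m criterion. The ventilator diary collects dates and reasons. New invasive ventilation is a serious adverse event, apart from short planned surgical support (Protocol 10.4.1.2). SAP Appendix A scores a move from no or non-invasive ventilation to invasive ventilation as worsening in the composite.
- **The stakes are modest.** Both endpoints are tertiary and descriptive, n is displayed, and the one specified hypothesis test is on the composite, which uses neither walking distance nor a change in spirometry.
- **Scoring 0 m is extreme.** A child who fails the criterion may still walk some distance.

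All of this stands, and it limits the point. It does not remove it: a falling n does not say why children left, other endpoints do not correct the 6MWT and FVC tables, and the documentation of missing PFTs has no planned use. The population makes such losses foreseeable, since Stage 1 admits children with worsening respiratory failure or loss of walking (Protocol 7.1).

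**Conclusion.** The point holds as a conditional weakness in two sets of tertiary tables and the plots that draw on them. A child tested at baseline may have no later 6MWT or PFT value because of the disease itself, and the plan then summarises only the children who remain. With about 5 children per Cohort 3 arm, one such child can change the apparent direction of the mean: +10 m observed against -22 to -82 m with that child at 0 m, for assumed baselines of 150 to 450 m and a gain of 10 m in the others. These are illustrations on assumed values, not estimates of a bias that has occurred. Neither the primary safety endpoint nor the composite test is affected, and the plan does not conceal the decline.

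**What to change.** In SAP 2.4.10 and 2.5.2, for every patient with a baseline 6MWT or PFT:

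1. Report at each visit the number untestable because of disease, separately from other missing values. Take invasive ventilation from the ventilator log. Check lost ambulation against GMFCS-E&R and the Motor Skills Checklist, which the protocol schedules at the same visits as the 6MWT. First reconcile the criterion of walking without an assistive device with Protocol 9.3.3.2, which allows one, so that lost ambulation has a single definition.
2. Add a companion median for 6MWT and for PFT with disease-untestable patients ranked worst. Keep the observed-only table beside it.
3. Treat any mean with 0 m imputed as an optional sensitivity display only.

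If only one item is adopted, it should be the count.

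The cost is SAP wording and a few table rows. The one real piece of work is a derived reason for a missing 6MWT, because the requirement to document missing assessments covers PFT but is not stated for the walk.

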2.5.3 Study day calculation

Based on study protocol, study Day 1 is the date of first study infusion (i.e., Week1 Day 1).

Study day for a given assessment is defined as the assessment date - date of first study infusion + 1 if the assessment date is on or after Day 1, or assessment date - date of first study infusion if the assessment date is before Day 1.

For cohort 3 patients, if a randomized patient is not treated (first infusion date is missing), study Day 1 is the date of randomization.

2.5.4 Windows for time points

The visit windows for efficacy endpoints are defined in the following table. For analysis purpose, a larger window (as shown in the last column of [Table 5](#)) will be used. This will be applicable for those analyses requiring visit information.

The analysis visit will be defined by comparing the actual visit date with the nominal (or target) date and the corresponding analysis window from [Table 5](#). If more than one non-missing value is assigned to the same visit, then the one closest to the target date will be used in the by-visit analysis. Multiple values on the same date will be averaged first. If two assessments are on different dates but equal distance from the target date, the later date will be used.

For the safety analyses (laboratory, ECG and vital signs), the nominal visit will be used for the by-visit type of analyses.

Table 5 - Study visit nominal visit days and windows for efficacy endpoints

Scheduled Visit	Visit window defined in protocol in study days	Visit window for analysis purpose in study days
Screening/Baseline	Day -14 to -1	-28 to -1 (or 1 if before 1st infusion)
Week 13	Day 85 ±14	Day 0 (or Day 2 if Screening/baseline on Day 1) to 85 + 41
Week 25	Day 169 ±14	Day 169- 42 to 169 + 41 and prior to any ETP treatment
Week 37	Day 253 ±14	Day 253- 42 to 253 + 41 and after the 1st ETP treatment
Week 49	Day 337 ±14	Day 337- 42 to 337 + 41
Week 61	Day 421 ±14	Day 421 - 42 to 421 + 41
Week 73	Day 505 ±14	Day 505 - 42 to 505 + 83
Week 97	Day 673 ±14	Day 673- 84 to 673 + 83
Week 121	Day 841 ±14	Day 841- 84 to 841 + 83
Week 145	Day 1009 ±14	Day 1009- 84 to 1009 + 83 ±84

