10.1.7 Follow-up for patients who temporarily or permanently discontinued the study treatment

- In case of temporary treatment discontinuation of study drug, the visits and assessments will be adapted to the absence of infusion of alglucosidase alfa until the patient resumes treatment within the study:
 - Study visits can be adapted to every 4 weeks or when laboratory and/or clinical testing are scheduled, as long as the assessment time windows in the study protocol are respected. Patients should adhere to original target infusion and visit schedule based on first infusion in the ACT14132 study.
 - As no infusion of IMP will be performed, no assessment of infusion-associated vital signs, as well as no PK sampling is required while the participant is temporarily withdrawn from treatment.
 - A patient who will be enrolled but will not receive the first infusion due to a concurrent reason or event not related to the study, will be considered as being temporarily discontinued from the study drug and the rules described above will apply.

- Reinitiation of treatment with IMP will be offered to the patient at the discretion of the Investigator and in agreement with the study participant, under close and appropriate clinical and/or laboratory monitoring.

Patients who permanently discontinue the study treatment prior to the scheduled Week 25 or after Week 25, but prior to the scheduled Week 145 visit, will have assessments corresponding respectively to Week 25 or Week 145 performed prior to or in combination with the safety assessment after last infusion (refer to [Section 10.1.4](#)). Patients who permanently discontinue the study treatment prior to the scheduled end of treatment during the extended long-term treatment period will have assessments corresponding to the end of treatment visit.

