If data is missing at Week 25, the score measured at precedent visit (Week 13) will be used.

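### For a patient who stops at about Week 13 to Week 17 and has no later PAP visit, the SAP's visit windows can drop the discontinuation assessment and let the older Week 13 score stand for Week 25 in the composite

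*SAP*

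**What the plan says.** Protocol 10.1.7 states that patients who permanently stop treatment early "will have assessments corresponding respectively to Week 25 or Week 145 performed prior to or in combination with the safety assessment after last infusion". Protocol 10.3.4 makes one discontinuation visit with the Week 25 procedures the minimum and allows it to be combined with the 4-week safety follow-up. The same section encourages stoppers to keep their scheduled PAP visits, but withdraws from the study those who switch to commercial alglucosidase alfa.

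SAP 2.5.4 sets the efficacy windows by date, not by visit label: "The analysis visit will be defined by comparing the actual visit date with the nominal (or target) date". In Table 5 the Week 13 window is "Day 0 (or Day 2 if Screening/baseline on Day 1) to 85 + 41" and the Week 25 window is "Day 169- 42 to 169 + 41 and prior to any ETP treatment". The rule for several values in a window is: "If more than one non-missing value is assigned to the same visit, then the one closest to the target date will be used". For ties, "If two assessments are on different dates but equal distance from the target date, the later date will be used".

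SAP 2.5.2 says of the composite: "If data is missing at Week 25, the score measured at precedent visit (Week 13) will be used". Continuous endpoints are summarised on observed data only. Neither SAP section mentions the discontinuation assessment.

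**The concern.** In the PAP flow chart (Protocol 1.2.1), GMFM-88, QMFT, Pompe-PEDI and echocardiography are scheduled only at screening/baseline, Week 13 and Week 25. For a patient who stops soon after Week 13 and is not seen again in the PAP, the discontinuation set is the only measurement of these endpoints after Week 13. The protocol calls it the Week 25 assessment; the SAP's dates make it a second Week 13 value.

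If it loses to the scheduled Week 13 value, it appears in no by-visit efficacy summary. The Week 25 window is then empty, and the composite takes the score from the earlier, on-treatment visit. This happens only to stoppers. Any change between Week 13 and stopping, in either direction, is left out of the Week 25 composite, which carries the study's one planned hypothesis test (SAP 3).

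**Working it through.** **Plan's own figures.** Nominal day = 7 × (week − 1) + 1. Week 13: 7 × 12 + 1 = Day 85. Week 25: 7 × 24 + 1 = Day 169. Both match Table 5.

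**Windows.** Week 13 ends on Day 85 + 41 = 126. Week 25 runs from Day 169 − 42 = 127 to Day 169 + 41 = 210. There is no gap or overlap.

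**Assumptions.**
- Infusions are every other week on nominal days, so infusion k falls on Day 1 + 14(k − 1). Weeks 13, 15, 17 and 19 are Days 85, 99, 113 and 127.
- The Week 13 efficacy assessment is on Day 85.
- The discontinuation visit falls 1 to 28 days after the last infusion. The documents do not fix this range; 28 days comes from the 4-week follow-up in Protocol 10.3.4.
- There is no later PAP visit.

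A discontinuation value is dropped if it falls on Day 126 or earlier and is further from Day 85 than the Week 13 value.

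| Last infusion | Discontinuation visit | Days on which it is dropped |
|---|---|---|
| Week 13, Day 85 | Day 86–113 | 28 of 28 |
| Week 15, Day 99 | Day 100–127 | 27 of 28 (only Day 127 reaches Week 25) |
| Week 17, Day 113 | Day 114–141 | 13 of 28 (Day 114–126) |
| Week 19, Day 127, or later | Day 128 onward | 0 |

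**Sensitivity to timing.**
- Protocol 10.1 has long visits start at least 7 days after the last infusion. With a range of 7 to 28 days, the counts are 22 of 22, 21 of 22 and 7 of 22.
- Protocol 10.1.6 lets follow-up shrink to 2 weeks. With a range of 1 to 14 days, the counts are 14 of 14 (Day 86–99), 14 of 14 (Day 100–113) and 13 of 14 (Day 114–127).
- Let the Week 13 value fall anywhere in its protocol window (Day 71–99), with a later discontinuation visit on Day 86–126. Then 979 of 1,084 date pairs (90%) drop the discontinuation value. The exceptions are early Week 13 visits: with Week 13 on Day 71, a discontinuation visit up to Day 99 is kept, the tie at Day 99 going to the later date. These pairs are counted equally, so 90% is not a probability for a patient.

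**Size in the composite.** Each domain moves by 1 point per step between improvement, unchanged and worsening (SAP Table 1). With 5 patients per arm, one patient wrong by one step in one domain shifts the arm mean by 1/5 = 0.2. The ceiling is two steps in all three domains: 6/5 = 1.2.

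**The case against.** The strongest reply is that the gap is narrow.

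- **Earlier stoppers.** A reader might infer that every early stopper loses the discontinuation set, because any set done by Day 126 lands in the Week 13 window. Landing there is not the same as being dropped. After a last infusion at Weeks 1 to 11 there is normally no competing on-treatment value, so the set is kept. It is labelled Week 13 and, in the composite, carried to Week 25.
- **Later stoppers.** From the Week 19 infusion on, the set falls in the Week 25 window and is used.
- **Continued follow-up.** The protocol's default is that stoppers are followed as scheduled (Clinical Trial Summary; 10.3.4). A patient who attends Week 25 supplies a true value, and the SAP uses it.
- **Data are not erased.** The selection rule ends with its own limit: "then the one closest to the target date will be used in the by-visit analysis". SAP 2.4.8 also plans patient profiles over time for all efficacy parameters, and nothing bars discontinuation values from them.
- **Stopping is reported elsewhere.** Adverse events leading to discontinuation are tabulated and listed (SAP 2.4.4.1), and PAP non-completion is reported with reasons (SAP 2.2).
- **Limited weight.** The primary objective is safety, and laboratory, ECG and vital-sign tables use nominal visits. SAP 1.5 makes the composite exploratory, and SAP 2.4.8 treats its p-values as references only.

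All of this stands, and it sets the scope of the point. It does not cover a patient who stops at about Week 13 to Week 17 and leaves the study, for example on switching to commercial alglucosidase alfa. For that patient the written rules choose the older value over the newer one.

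**Conclusion.** The point holds within those limits. It needs three things together: a last PAP infusion at about Week 13 to Week 17, a Week 13 value closer to Day 85 than the discontinuation visit, and no later PAP visit. The counts rest on nominal visit days and an assumed 28-day limit; a 2-week follow-up would raise the Week 17 share.

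How many patients this affects cannot be calculated, because the documents give no discontinuation rate; it may be none. The 0.2 shift is what one such patient could cause in an arm of 5, not an expected bias.

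Two wider readings are not supported. One is that the primary safety evaluation is compromised: the date windows apply to efficacy endpoints only. The other is that early Week 145 assessments in the extension are lost in the same way: those windows are different and no calculation here covers them.

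This is a cheap improvement worth making, because the rules as written set aside the latest outcome in a selected group.

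**What to change.** In SAP 2.5.4, define the PAP discontinuation assessment as a separate, flagged analysis visit that does not compete under the closest-to-target rule. In SAP 2.5.2, when the Week 25 window is empty, take the composite from the latest post-baseline PAP assessment, including the discontinuation assessment, instead of from Week 13.

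The cost is two wording changes and one derived visit, with no new data. The small downside is that the carried value is measured at a variable time.
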